#### Table 14.3.2.6.2 TEAEs of special interest by Maximum Severity, System Organ Class and Grouped Preferred Term (As Treated Population)

N = number of patients in analysis set; n = number of patients with data available; % = percentages are calculated based on N as the denominator; E = number of events. TEAE = Treatment Emergent Adverse Event.

Note: TEAEs are events with start date on or after the date of first dose of any study drug or events with start date prior to the date of first dose of any study drug whose severity worsens on or after the date of first dose of any study drug. If the event started on the date of first dose of the first study drug administration however it is ticked as the event started prior to first study drug administration on Day 1 in the eCRF, it is not considered as a TEAE.

Adverse events were assigned severity grade using the Common Terminology Criteria for Adverse Events (CTCAE) Version 5.0.

[a] Within a system organ class, patients may have reported more than one grouped preferred term. Patients are counted once for each grouped preferred term and each system organ class.

[b] Patients with multiple events within a particular SOC or PT will be counted under the category of their most severe event within that SOC or PT.

MedDRA version & meddra.

Reference: Listing 16.2.7.4

Programming notes (not part of the table):

• Table template TAE005.

• Sort alphabetically by system organ class and descending grouped preferred term in the total column. Where grouped preferred terms tie these should be sorted alphabetically.

Assign the version of MedDRA Dictionary to &meddra. macro variable as XX.X and update the version of MedDRA Dictionary used for coding as needed.

• If a patient experienced more than one AE within the same SOC and PT, the AE with the maximum intensity should be counted for that SOC and PT.

# 3.13 Laboratory Data

#### Table 14.3.4.1 Summary of Laboratory Results - Haematology (As Treated Population)

#### Parameter (unit)

	Plitidepsi (N=X	n 2.5mg XX)	Plitideps (N=X	in 1.5mg (XX)	Plitideps (N=X	sin Total XXX)	Contro (N=X	ol Arm XXX)
Visit	X 7-1 4 X 7*-*4	Change from	X7-1	Change from	X 7-1 4 X 7**4	Change from	X 7-1 4 X 7**4	Change from
Statistic	value at visit	Baseline	value at visit	Baseline	value at visit	Baseline	value at visit	Baseline
Baseline								
n	XXX		XXX		XXX		XXX	
Mean (SD)	xx.xx (xx.xxx)		xx.xx (xx.xxx)		xx.xx (xx.xxx)		xx.xx (xx.xxx)	
Median	XX.XX		XX.XX		XX.XX		XX.XX	
Q1, Q3	xx.xx, xx.xx		xx.xx, xx.xx		xx.xx, xx.xx		xx.xx, xx.xx	
Min, Max	xx.x, xx.x		xx.x, xx.x		xx.x, xx.x		xx.x, xx.x	
< <day x="">></day>								
n	XXX	XXX	XXX	XXX	XXX	XXX	XXX	XXX
Mean (SD)	xx.xx (xx.xxx)	xx.xx (xx.xxx)	xx.xx (xx.xxx)	xx.xx (xx.xxx)	xx.xx (xx.xxx)	xx.xx (xx.xxx)	xx.xx (xx.xxx)	xx.xx (xx.xxx)
Median	XX.XX	XX.XX	XX.XX	XX.XX	XX.XX	XX.XX	XX.XX	XX.XX
Q1, Q3	xx.xx, xx.xx	xx.xx, xx.xx	xx.xx, xx.xx	xx.xx, xx.xx	xx.xx, xx.xx	xx.xx, xx.xx	xx.xx, xx.xx	xx.xx, xx.xx
Min, Max	XX.X, XX.X	xx.x, xx.x	xx.x, xx.x	xx.x, xx.x	xx.x, xx.x	xx.x, xx.x	xx.x, xx.x	XX.X, XX.X
etc.								

N = number of patients in analysis set; n = number of patients with data available.

SD = Standard deviation; Q1 = 25th percentile; Q3 = 75th percentile; Min = Minimum; Max = Maximum.

Notes: The Baseline value is defined as last scheduled or unscheduled non-missing value from central Laboratory collected prior to the first dose of the first study drug administration. Reference: Listing 16.2.8.1.1

- Table template TLB004B.
- Parameters are: Red Blood Cell Count, Haemoglobin, Haematocrit, White Blood Cell Count, Neutrophils, Eosinophils, Basophils, Lymphocytes, Monocytes, and Platelet Count.
- Visits: Day 2, Day 3, Day 4, Day 8, and Day 31.
- The displayed xxx do not reflect actual decimal precision. Please follow Section 2.11 for rounding rules.

#### Table 14.3.4.2 Summary of Laboratory Results - Serum Chemistry (As Treated Population)

#### Parameter (unit)

	Plitidepsi (N=X	n 2.5mg XX)	Plitideps (N=X	sin 1.5mg XXX)	Plitideps (N=X	sin Total XXX)	Contro (N=X	Control Arm (N=XXX)	
Visit		Change from		Change from		Change from		Change from	
Statistic	Value at Visit	Baseline	Value at Visit	Baseline	Value at Visit	Baseline	Value at Visit	Baseline	
Baseline									
n	XXX		XXX		XXX		XXX		
Mean (SD)	xx.xx (xx.xxx)		xx.xx (xx.xxx)		xx.xx (xx.xxx)		xx.xx (xx.xxx)		
Median	XX.XX		XX.XX		XX.XX		XX.XX		
Q1, Q3	XX.XX, XX.XX		xx.xx, xx.xx		xx.xx, xx.xx		xx.xx, xx.xx		
Min, Max	xx.x, xx.x		xx.x, xx.x		xx.x, xx.x		xx.x, xx.x		
< <day x="">></day>									
n	XXX	XXX	XXX	XXX	XXX	XXX	XXX	XXX	
Mean (SD)	xx.xx (xx.xxx)	xx.xx (xx.xxx)	xx.xx (xx.xxx)	xx.xx (xx.xxx)	xx.xx (xx.xxx)	xx.xx (xx.xxx)	xx.xx (xx.xxx)	xx.xx (xx.xxx)	
Median	XX.XX	XX.XX	XX.XX	XX.XX	XX.XX	XX.XX	XX.XX	XX.XX	
Q1, Q3	xx.xx, xx.xx	xx.xx, xx.xx	xx.xx, xx.xx	xx.xx, xx.xx	xx.xx, xx.xx	xx.xx, xx.xx	xx.xx, xx.xx	xx.xx, xx.xx	
Min, Max	xx.x, xx.x	xx.x, xx.x	xx.x, xx.x	xx.x, xx.x	xx.x, xx.x	xx.x, xx.x	xx.x, xx.x	xx.x, xx.x	
etc.									

N = number of patients in analysis set; n = number of patients with data available.

SD = Standard deviation; Q1 = 25th percentile; Q3 = 75th percentile; Min = Minimum; Max = Maximum.

Notes: The Baseline value is defined as last scheduled or unscheduled non-missing value from central Laboratory collected prior to the first dose of the first study drug administration. Reference: Listing 16.2.8.1.2

- Table template TLB004B.
- Parameters are: Alanine aminotransferase (ALT), Aspartate aminotransferase (AST), Alkaline phosphatase, Gamma-Glutamyltransferase (GGT), Total Bilirubin, Direct Bilirubin, Glucose (fasting), Sodium, Potassium, Calcium (adjusted), Magnesium, Creatinine, Calculated Creatinine Clearance (Cockcroft Gault equation), Albumin, Creatine Phosphokinase (CPK), Troponin T, N-terminal pro b-type natriuretic peptide (NT-pro-BNP), Blood Urea Nitrogen, Amylase, Lipase, and Procalcitonin.
- Visits: Day 2, Day 3, Day 4, Day 8, and Day 31.
- The displayed xxx do not reflect actual decimal precision. Please follow Section 2.11 for rounding rules.

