- Hypertension at Screening, defined as Hypertension (Standardised MedDRA Query [SMQ]) in the Medical History form: Yes or No
- Individual co-morbidities included in the Charlson Index: myocardial infarction (Yes or No), congestive heart failure (Yes or No), peripheral vascular disease (Yes or No), cerebrovascular disease (Yes or No), dementia (Yes or No), chronic obstructive pulmonary disease (Yes or No), connective tissue disease (Yes or No), peptic ulcer disease (Yes or No), liver disease ('None', 'Mild' or 'Moderate or Severe'), diabetes mellitus ('None or diet controlled', 'Uncomplicated' or 'End-organ damage'), hemiplegia (Yes or No), moderate or severe chronic kidney disease (Yes or No), solid tumor ('None', 'Localized' or 'Metastatic'), leukemia (Yes or No), lymphoma (Yes or No) or AIDS (Yes or No).
- ISARIC-4C mortality score: Low (0 3), Intermediate (4 8), High (9 14) or Very high (≥ 15)
- ISARIC-4C deterioration probability (%): `≤ 25', `(25 50]', or `> 50'
- Lactate dehydrogenase (LDH) at Baseline: ≤ ULN or > ULN

- CRP (mg/L) at Baseline: ≤ 100 or > 100
- D-dimer at Baseline: ≤ ULN or > ULN
- Ferritin at Baseline: ≤ ULN or > ULN
- Creatinine at Baseline: ≤ ULN or > ULN
- IL-6 at Baseline: ≤ Median or > Median value (at the analysis time cutoff may be updated based on distribution values if needed)
- IL-10 at Baseline: ≤ Median or > Median value (at the analysis time cutoff may be updated based on distribution values if needed)
- Lymphocytes count decreased at Baseline: 'Grade 0' or 'Grade  $\geq 1'$
- Neutrophils/lymphocytes ratio at Baseline:  $< 6 \text{ or } \ge 6$
- SARS-CoV-2 variant: Alpha, Beta, Gamma, Delta, Eta, Iota, Kappa, Lambda, Mu, or any potential new variant

The same covariates used for the primary efficacy endpoint analysis will be used for the subgroup analyses.

For ISARIC-4C mortality score and deterioration probability calculation:

- A Glasgow coma scale score of 15 is assumed for all the patients.
- Urea (mmol/L) will be calculated as blood urea nitrogen (mmol/L) \* 60 / 28.

Forest plots of the hazard ratios, and the 95% CI for the comparison of each dose of plitidepsin versus control arm will be presented by endpoint for all subgroups using the ITT population.

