### 7.7.3 Laboratory Evaluations

Data for the haematology, serum chemistry, and coagulation analytes received from central laboratory will be listed and summarized by treatment group and overall plitidepsin, and visit. Haematology and serum chemistry analytes from local laboratories recorded at Screening in the eCRF will be listed only. If data for any additional analytes are also received then these will be listed only.

Immunology and Serological SARS CoV 2 data are summarised within the other secondary efficacy endpoints.

Haematology	Serum Chemistry	
Red Blood Cell Count	Alanine aminotransferase (ALT)	
Haemoglobin	Aspartate aminotransferase (AST)	
Haematocrit	Alkaline phosphatase	
White Blood Cell Count	Gamma-Glutamyltransferase (GGT)	
Neutrophils	LDH	
Eosinophils	Total Bilirubin	
Basophils	Direct Bilirubin	
Lymphocytes	Glucose (fasting)	
Monocytes	Sodium	
Platelet Count	Potassium	
Transunalagy	Calcium (adjusted)	
Immunology	Magnesium	
CRP	Blood Urea Nitrogen	
Ferritin	Creatinine	
IL-1β	Calculated Creatinine Clearance (Cockcroft-Gault equation)	
IL-6	Creatine Phosphokinase (CPK)	
IL-10	Albumin	
TNFa	Amylase	
	Lipase	
Other Samples	Procalcitonin	
Pregnancy tests (females	Troponin T	
only)	N-terminal pro-B-type natriuretic peptide (NT-pro-BNP)	
Coagulation	Serological SARS CoV 2 testing	
D-dimer	IgG	

All central Laboratory data will be reported in International System of Units. Local Laboratory data will be listed in the Units that they were collected in the eCRF. Outof-reference-range values will be flagged as high (H) or low (L) in the listings. For analysis purposes, values preceded by a "<" or a ">" sign (ie, those below or above the limits of quantification) will be considered equal to the lower or upper limit of quantification, respectively.

Central laboratory data will be summarized by visit using standard descriptive statistics by treatment group and overall plitidepsin for the As Treated population. Changes from Baseline will also be summarized. For post-Baseline, only data from scheduled visits will be included in the summary tables.

If more than 10% of the patients preform an unscheduled central laboratory assessment at the same relative day to the start date of study treatment then the central laboratory data will be also summarised at the specific relative day. In case of several unscheduled laboratory assessments at the same day we will use the worst result.

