- **6** Serum chemistry: *Prestudy screening assessments*: ALT, AST, total bilirubin, sodium, potassium, calcium (albumin adjusted), magnesium, creatinine, calculated creatinine clearance (Cockcroft-Gault equation), CPK, and troponin (I or T according to local practice). *On study assessments*: ALT, AST, alkaline phosphatase, GGT, LDH, total bilirubin, direct bilirubin, glucose (fasting), sodium, potassium, calcium (albumin adjusted calculation), magnesium, blood urea nitrogen, creatinine, calculated creatinine clearance (Cockcroft-Gault equation), CPK, albumin, amylase, lipase, procalcitonin, troponin T (high sensitivity), and NT-pro-BNP. Note that testing to be performed by the local laboratory for screening and by central laboratory for on-study tests; tests performed within 24 hours of screening do not have to be repeated. All serum chemistry parameters will be measured at Day 1 prior to initiation of study treatment, once daily during hospitalisation, and at follow-up visits on Days 8 (±1 day) and 31 (±3 days); except, troponin T (high sensitivity), and NT-pro-BNP that will be measured on Day 1, Day 8 (±1 day), and Day 31 (±3 days).
- 7 Coagulation: D-dimer
- 8 Immunology: Proinflamatory biomarkers (CRP, ferritin, IL-1β, IL-6, IL-10, TNFα) in each study arm from baseline (Day 1 prior to start of the study treatment) to Day 4 and Days 8 (±1 day), 15 (±1 day) and 31 (±3 days).
- 9 COVID-19 screen: Qualitative PCR, antigen test to be performed by local laboratory, or any other validated method approved by the local health authority, from appropriate biological samples collected no more than 72 hours before study treatment on Day 1 for screening test to confirm COVID-19. In case more than one available, the more recent one will be selected.
- 10 COVID-19 viral load: Quantitative real-time reverse transcription polymerase-chain-reaction test (qRT-PCR) test to be performed by central laboratory from oro-nasopharyngeal exudate on Day 1 prior to initiating treatment and on Day 8 (±1 day).
- 11 Chest imaging: CT scan or x-ray will be done on Days 1, 8 (±1 day), and 31 (±3 days). Chest imaging performed within 48 hours of Day 1 is accepted and does not have to be repeated
- 12 Pregnancy test: Serum or urine pregnancy test for females of child-bearing potential, to be performed by local laboratory for screening

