- Parameters are: Alanine aminotransferase (ALT) High, Aspartate aminotransferase (AST) High, Alkaline phosphatase High, Gamma-Glutamyltransferase (GGT) High, Lactate dehydrogenase (LDH) High, Total Bilirubin High, Glucose (fasting) Low, Sodium Low, Sodium High, Potassium Low, Potassium High, Calcium Low, Calcium High, Magnesium Low, Magnesium High, Creatinine High, Albumin Low, Creatine Phosphokinase (CPK) High, Troponin T High, Amylase High, and Lipase High.

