# 3.17 Safety subgroup analyses

#### Table 14.3.8.1 Summary of TEAEs and Clinically Relevant Laboratory Tests - Worst Grade Post-Baseline - Subgroup Analysis (As Treated Population)

< <subgroup>></subgroup>								
	Plitidepsin (N=XX	2.5mg (X)	Plitidepsin (N=XX	1.5mg (X)	Plitidepsir (N=XX	n Total XX)	Control (N=X)	Arm XX)
	Grade >=1 or (>=ULN if not NCI-CTCAE		Grade >=1 or (>=ULN if not NCI-CTCAE		Grade >=1 or (>=ULN if not NCI-CTCAE		Grade >=1 or (>=ULN if not NCI-CTCAE	
Laboratory Abnormality/	grade)	Grade >=3	grade)	Grade >=3	grade)	Grade >=3	grade)	Grade >=3
TEAE	n (%)	n (%)	n (%)	n (%)	n (%)	n (%)	n (%)	n (%)
CTCAE: Anemia	xxx (xx.x)	xxx (xx.x)	xxx (xx.x)	xxx (xx.x)	xxx (xx.x)	xxx (xx.x)	xxx (xx.x)	xxx (xx.x)
CTCAE: Platelet count	xxx (xx.x)	xxx (xx.x)	xxx (xx.x)	xxx (xx.x)	xxx (xx.x)	xxx (xx.x)	xxx (xx.x)	xxx (xx.x)
decreased								
CTCAE: Neutrophil count	xxx (xx.x)	xxx (xx.x)	xxx (xx.x)	xxx (xx.x)	xxx (xx.x)	xxx (xx.x)	xxx (xx.x)	xxx (xx.x)
decreased	. .		.		, ,		.	
CTCAE: AP increased	xxx (xx.x)	xxx (xx.x)	xxx (xx.x)	xxx (xx.x)	xxx (xx.x)	xxx (xx.x)	xxx (xx.x)	xxx (xx.x)
CTCAE: Blood bilirubin	xxx (xx.x)	xxx (xx.x)	xxx (xx.x)	xxx (xx.x)	xxx (xx.x)	xxx (xx.x)	xxx (xx.x)	xxx (xx.x)
increased	( )	.				.	( )	, , , , , , , , , , , , , , , , , , ,
CTCAE: AST increased	XXX (XX.X)	xxx (xx.x)	XXX (XX.X)	XXX (XX.X)	XXX (XX.X)	XXX (XX.X)	XXX (XX.X)	xxx (xx.x)
CTCAE: ALT increased	xxx (xx.x)	xxx (xx.x)	xxx (xx.x)	xxx (xx.x)	xxx (xx.x)	xxx (xx.x)	xxx (xx.x)	xxx (xx.x)
CTCAE: CPK increased	xxx (xx.x)	xxx (xx.x)	xxx (xx.x)	xxx (xx.x)	xxx (xx.x)	xxx (xx.x)	xxx (xx.x)	xxx (xx.x)
CTCAE: LDH increased	xxx (xx.x)	NA	xxx (xx.x)	NA	xxx (xx.x)	NA	xxx (xx.x)	NA
Ferritin	xxx (xx.x)	NA	xxx (xx.x)	NA	xxx (xx.x)	NA	xxx (xx.x)	NA
D-dimer	xxx (xx.x)	NA	xxx (xx.x)	NA	xxx (xx.x)	NA	xxx (xx.x)	NA
TEAE: Nausea	xxx (xx.x)	xxx (xx.x)	xxx (xx.x)	xxx (xx.x)	xxx (xx.x)	xxx (xx.x)	xxx (xx.x)	xxx (xx.x)
TEAE: Vomiting	xxx (xx.x)	xxx (xx.x)	xxx (xx.x)	xxx (xx.x)	xxx (xx.x)	xxx (xx.x)	xxx (xx.x)	xxx (xx.x)
TEAE: Fatigue	xxx (xx.x)	xxx (xx.x)	xxx (xx.x)	xxx (xx.x)	xxx (xx.x)	xxx (xx.x)	xxx (xx.x)	xxx (xx.x)
TEAE: xxxxxxxxxx [a]	xxx (xx.x)	xxx (xx.x)	xxx (xx.x)	xxx (xx.x)	xxx (xx.x)	xxx (xx.x)	xxx (xx.x)	xxx (xx.x)

N = number of patients in analysis set within the subgroup; n = number of patients with data available; % = percentages are calculated based on N as the denominator.

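### The by-visit chemistry table omits LDH, although SAP Section 7.7.3 includes it among the analytes to be summarised by visit and arm

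*SAP*

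**What the plan says.** Section 7.7.3 of the SAP sets the general rule for laboratory data: "Data for the haematology, serum chemistry, and coagulation analytes received from central laboratory will be listed and summarized by treatment group". It then gives the form of the summary: "Central laboratory data will be summarized by visit using standard descriptive statistics by treatment group and overall plitidepsin for the As Treated population", followed by "Changes from Baseline will also be summarized". LDH stands in that section's serum chemistry list. It is also collected on study with the rest of the panel: the serum chemistry footnote to the schedule of assessments (Appendix 4) reads "ALT, AST, alkaline phosphatase, GGT, LDH, total bilirubin, direct bilirubin, glucose (fasting". Section 3.4 lists actual values and change from baseline in clinical laboratory results as a safety endpoint.

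The TFL shells implement the by-visit chemistry summary in Table 14.3.4.2. Its programming note lists the parameters, and the stretch where LDH would be expected reads "Gamma-Glutamyltransferase (GGT), Total Bilirubin, Direct Bilirubin, Glucose (fasting), Sodium".

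LDH does appear elsewhere:
- in the worst-grade shift table, Table 14.3.4.5, as "Lactate dehydrogenase (LDH) High";
- in the safety subgroup table, Table 14.3.8.1, as "CTCAE: LDH increased", with the Grade 3 or higher cells shown as NA in every arm;
- as an efficacy subgroup in Section 7.6.4, "Lactate dehydrogenase (LDH) at Baseline: ≤ ULN or > ULN", and with the same cut as a covariate in the multivariate models;
- in Listing 16.2.8.1.2, patient by patient.

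**The concern.** The SAP text and the programming instruction that is meant to carry it out disagree on one analyte. A programmer working from the shell would produce the chemistry table without LDH, and nothing in the shell would signal that a promised summary had been lost. Part of a declared safety endpoint would then be missing from the by-arm summaries, with no recorded reason. A reader comparing the doses with control on LDH would have to rebuild the comparison from individual listing rows.

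**Working it through.** No power, alpha or sample size figure is involved. The check compares lists and then traces every LDH output.

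**Step 1. Count the promised analytes.** The serum chemistry list in Section 7.7.3 holds ALT, AST, alkaline phosphatase, GGT, LDH, total bilirubin, direct bilirubin, glucose, sodium, potassium, adjusted calcium, magnesium, blood urea nitrogen, creatinine, calculated creatinine clearance, CPK, albumin, amylase, lipase, procalcitonin, troponin T and NT-pro-BNP: 22 analytes.

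**Step 2. Count the table parameters.** The Table 14.3.4.2 note lists 21.

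**Step 3. Compare the two sets.** In Section 7.7.3 but not in the table: LDH only. In the table but not in Section 7.7.3: none. So 22 − 21 = 1, and the whole difference is LDH.

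**Step 4. Compare the companion listing.** Listing 16.2.8.1.2 has 23 parameters: all 22 from Section 7.7.3 plus ferritin. It places LDH between GGT and total bilirubin, which is where the table note skips it.

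**Step 5. Look for another by-visit LDH summary.**

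| Output | What it gives for LDH |
|---|---|
| Table 14.3.4.2 (chemistry by visit) | Nothing |
| Table 14.3.4.5 (grade shifts) | Worst post-baseline grade against baseline grade; no visit, no size of change |
| Table 14.3.8.1 (safety subgroups) | Count at Grade 1 or higher; Grade 3 or higher shown as NA |
| Table 14.2.3.20 (biomarkers) | Not included |
| Figures 14.3.4.1.1 and 14.3.4.1.2 | Not included |
| Section 7.6.4 subgroup, forest plots, multivariate models | Baseline only, cut at ULN |
| Listing 16.2.8.1.2 | Individual values and changes; no statistics by arm |
| SAP addendum | No by-visit LDH summary added |

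Summary tables or figures that give LDH values or changes by arm and visit: 0.

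**Step 6. Look for a recorded decision.** Section 8, Changes in Planned Analysis, does not mention LDH. Appendix 1 of the shells gives LDH a unit and a precision (U/L, no decimals), and Section 2.11.1 of the shells refers to that appendix for rounding the continuous laboratory parameters. Together with the listing and the shift table, this points to an oversight rather than a choice.

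**Step 7. Check the fix.** 21 + 1 = 22, which then matches Section 7.7.3 exactly.

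**The case against.** The introduction to the shells describes them as guidance for the programmers and statisticians, and Section 7.7.3 already commits to the summary. On that view the SAP text governs and LDH may well be produced despite the note. This stands as a limit: the documents show a contradiction and what follows if the note is taken literally; they do not show that the output was lost.

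Several stronger readings are tempting, and the documents do not carry them.

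- A reader might infer from the NA cells in Table 14.3.8.1 that LDH grading is only normal against abnormal, so that a further rise in patients already above normal would be invisible. Those cells concern only Grade 3 or higher. The Table 14.3.4.5 shell has columns for Grades 0 to 4, and the LDH cut-offs are printed nowhere in the document. A move between lower grades could show in the shift table.
- A reader might want to say what share of patients could show an upward shift. That needs both the grade cut-offs and the proportion entering above ULN; the SAP gives neither.
- A reader might tie LDH to the muscle and liver events of special interest. The definitions in Section 7.7.2 do not name it, and CPK, ALT, AST, alkaline phosphatase, GGT, bilirubin and troponin T all remain in Table 14.3.4.2.
- Absence from the laboratory plots is not a second contradiction. Section 7.7.3 selects specific measures for plotting, and LDH is not among them.
- The listing supports the reading of an oversight but does not itself oblige a summary table: it also carries ferritin, which Table 14.3.4.2 properly leaves out.

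**Conclusion.** The contradiction holds. Section 7.7.3 promises a by-visit, by-arm summary of LDH and its change from baseline; the parameter list of the only table that would supply it leaves LDH out, and no decision to drop it is recorded. The size is 1 of 22 serum chemistry analytes. The practical consequence rests on one assumption, that the shell note is followed as written; in that case LDH values and changes by arm and visit reach no summary output and survive only in the patient listing. The primary and key secondary analyses do not depend on this table, so no efficacy conclusion is affected. This is a minor inconsistency worth correcting because the correction is simple.

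**What to change.** Add Lactate Dehydrogenase (LDH) after GGT in the parameter list of Table 14.3.4.2, so that the shell matches Section 7.7.3. If the omission was intended, state it with the reason in Section 8 and amend Section 7.7.3. The cost is one more parameter in an existing program; the data are already collected and listed, and no new method or table is needed. The SAP addendum offers a route: it already corrects a label in several existing outputs and allows for additional tables.

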### Table 14.3.4.3 Summary of Laboratory Results - Coagulation (As Treated Population)

#### **D-dimer (unit)**

	Plitidepsi (N=X	n 2.5mg XX)	Plitideps (N=X	sin 1.5mg XXX)	Plitideps (N=X	sin Total XXX)	n Total Control Arm XX) (N=XXX)	
Visit		Change from		Change from		Change from		Change from
Statistic	Value at Visit	Baseline	Value at Visit	Baseline	Value at Visit	Baseline	Value at Visit	Baseline
Baseline								
n	XXX		XXX		XXX		XXX	
Mean (SD)	xx.xx (xx.xxx)		xx.xx (xx.xxx)		xx.xx (xx.xxx)		xx.xx (xx.xxx)	
Median	XX.XX		XX.XX		XX.XX		XX.XX	
Q1, Q3	XX.XX, XX.XX		xx.xx, xx.xx		xx.xx, xx.xx		xx.xx, xx.xx	
Min, Max	xx.x, xx.x		xx.x, xx.x		xx.x, xx.x		xx.x, xx.x	
< <day x="">></day>								
n	XXX	XXX	XXX	XXX	XXX	XXX	XXX	XXX
Mean (SD)	xx.xx (xx.xxx)	xx.xx (xx.xxx)	xx.xx (xx.xxx)	xx.xx (xx.xxx)	xx.xx (xx.xxx)	xx.xx (xx.xxx)	xx.xx (xx.xxx)	xx.xx (xx.xxx)
Median	XX.XX	XX.XX	XX.XX	XX.XX	XX.XX	XX.XX	XX.XX	XX.XX
Q1, Q3	XX.XX, XX.XX	XX.XX, XX.XX	xx.xx, xx.xx	xx.xx, xx.xx	xx.xx, xx.xx	xx.xx, xx.xx	xx.xx, xx.xx	XX.XX, XX.XX
Min, Max	XX.X, XX.X	XX.X, XX.X	xx.x, xx.x	XX.X, XX.X	xx.x, xx.x	XX.X, XX.X	xx.x, xx.x	XX.X, XX.X
etc.								

N = number of patients in analysis set; n = number of patients with data available.

SD = Standard deviation; Q1 = 25th percentile; Q3 = 75th percentile; Min = Minimum; Max = Maximum.

Notes: The Baseline value is defined as last scheduled or unscheduled non-missing value from central Laboratory collected prior to the first dose of the first study drug administration. Reference: Listing 16.2.8.1.4

Programming notes (not part of the table):

- Table template TLB004B.
- Visits: Day 2, Day 3, Day 4, Day 8, and Day 31.

• The displayed xxx do not reflect actual decimal precision. Please follow Section 2.11 for rounding rules.

